9.2.4.6 Data Collection

IMS will coordinate data collection with each site. At study initiation (Baseline, D0), patients will be asked to provide their written informed consent. After signing consent, the patients' questionnaires as recorded will be collected. At Week 12 and 24 time-

points, the patients' questionnaires will be collected before them visiting their physicians. There will be a study coordinator or study nurse at each site to monitor the process. The study coordinator/nurse will collect the record of questionnaires directly. Physicians will not see the contents patients entered. The study coordinator/nurse will check to ensure all the forms are filled-in correctly.

In addition, physicians will also be asked to complete a clinical CRF in paper form based on the patient's medical records at baseline, 12 weeks, and 24 weeks. The CRF completed by physicians will be returned to the study coordinator/nurse at each site as well.

All data will be collected by the study coordinator/nurse at each site and returned directly to IMS. The data collection time is expected to be 10-13 months.

All patient and clinician data will be handled preserving confidentiality.

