The patient treatment satisfaction questions were developed de novo for this study and are not considered "validated" questions. Self-administered by the patient, the completion time for the patient treatment satisfaction questions is approximately 1-2 minutes. The full version of patient treatment satisfaction questions are presented in Appendix I.

Healthcare Resource Utilization (HCRU) Questionnaire

The HCRU questionnaire will collect data on the healthcare resources consumed in the prior 3 months, as recall beyond 3 months may be problematic in an older population (16). HCRU collection will include data such as the number of physician visits and to which physician (GP, specialist), Emergency Department visits, hospitalizations, and other drugs as well as devices and aids purchased to assist in their mobility due to RA. The HCRU questionnaire will be part of the patient questionnaire and will be distributed to patients together with the PRO questionnaires (Appendix D to Appendix I). The full HCRU questionnaire is presented in Appendix J.

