Appendix C. Clinical Case Report Form (CRF)

Baseline:

1023259 Real-World Impact of RA
[Site number] - [Participant ID]

Clinician Case Report Form (Baseline)

All of the following information must be completed by the clinician or his/her representative.

Clinician name: _____

Clinician signature: _____

Patient ID	[Site #]	-	[Participant #]		
Today's date	[Day]	/	[Month]	/	[Year]

Please provide the information below.	
1. When was the patient diagnosed with Rheumatoid Arthritis?	[Year]
2. What is the patient's current disease status?	 Moderate  Severe

1023259 Real-World Impact of RA
 -
Site number Participant ID

Please provide the information below.		
3. Please perform a swollen and tender joint examination on your patient using the figure below and record the total number of tender/swollen joints in the appropriate boxes on the right.	 Tender Joint Count	 Swollen Joint Count
If diagnosis is RA:		
4. Please record the most recent Erythrocyte Sedimentation Rate (ESR) (in mm/hour) or C-reactive protein (CRP) (in mg/L) of this patient.	 ESR (mm/hour) Test Date (DD/MM/YYYY): ____/____/_____  CRP (mg/L) Test Date (DD/MM/YYYY): ____/____/_____ 5. Please record the latest DAS28 score*, if calculated	

* For calculation instruction, please refer to study protocol, page 21, clinical case report form (CRF).

1023259 Real-World Impact of RA
[REDACTED]
[REDACTED]
Site number - Participant ID

6. Please check all the comorbidities this patient has currently.

- ₀ No comorbidity
- ₁ Myocardial infarction
- ₂ Congestive heart failure
- ₃ Peripheral vascular disease
- ₄ Cerebrovascular disease
- ₅ Dementia
- ₆ Chronic pulmonary disease
- ₇ Connective tissue disease
- ₈ Ulcer disease
- ₉ Mild liver disease
- ₁₀ Diabetes
- ₁₁ Hemiplegia
- ₁₂ Moderate or severe renal disease
- ₁₃ Diabetes with end-organ damage
- ₁₄ Any tumor
- ₁₅ Leukemia
- ₁₆ Lymphoma
- ₁₇ Moderate or severe liver disease
- ₁₈ Metastatic solid tumor
- ₁₉ AIDS

1023259 Real-World Impact of RA
[REDACTED]
Site number - Participant ID

7. Please check all the prior medications this patient has received for her/his Rheumatoid Arthritis in the last 6 months.
(No response option for biologics is given as the current study recruits only patients with no history of any biologics prior to the study).

Drug Name	Average number of pills per day	Dose strength	Times per month

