Appendix J. Healthcare resource utilization (HCRU) questionnaire

Baseline:

1023259 Real-World Impact of RA

Site number	-	Participant ID
-------------	---	----------------

Healthcare Resource Utilization & Demographic Questionnaire (Baseline)

Patient ID	

Site #	-	Participant #	

	Site #	-	Participant #		
Site #	-	Participant #				
Today's date	

Day	/	Month	/	Year	

	Day	/	Month	/	Year
Day	/	Month	/	Year		

<Request on entering>

1. Please use ballpoint pen.
2. On selecting the item, please check surely in or enter into ().
3. On correcting, please cross out with a double line (=) and **initial and date**.

1023259 Real-World Impact of RA
[Site number] - [Participant ID]

1. When did you first start experiencing the symptoms of rheumatoid arthritis?

₀ Do not remember

₁ Year: _____

2. When did you first start visiting healthcare professionals for treatment of your rheumatoid arthritis ?

₀ Do not remember

₁ Year: _____

3. In the last 6 months, were there any consultations/visits to healthcare professionals for treatment of your rheumatoid arthritis? (Check all that apply)

₀ No visit in the last 6 months

₁ Yes →

₁ General Practitioner

(Taiwan: Family Medicine) _____ times

₂ Rheumatologist _____ times

₃ Gerontologist _____ times

₄ Orthopedist _____ times

₅ Internist _____ times

₆ Emergency department _____ times

₇ Traditional Medicine _____ times

₈ Physical therapist _____ times

(Taiwan: Rehabilitation Medicine) _____ times

₉ Other: _____ times

1023259 Real-World Impact of RA

Site number	-	Participant ID
-------------	---	----------------

4. In the last 6 months, when you visited the healthcare professional(s) for treatment of your rheumatoid arthritis, were there any procedures performed?

No, consultation only

Yes → Chest X-Ray _____ times
 Spine X-Ray _____ times
 Neck X-Ray _____ times
 Shoulder X-Ray _____ times
 Hand X-Ray _____ times
 Knee X-Ray _____ times
 MRI _____ times
 CT scan _____ times
 Electrocardiogram _____ times
 Blood sample taken _____ times
 Urine test _____ times
 Endoscopy _____ times
 Bone scan _____ times
 Liver function test _____ times
 Tuberculin Skin Test _____ times
 Sputum tests _____ times
 Other: _____ times

1023259 Real-World Impact of RA
[REDACTED]
Site number - Participant ID

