 ₁₃ Aspirin (ASA)	_____	_____ mg	_____
 ₁₄ Diclofenac (Voltaren)	_____	_____ mg	_____

1023259 HCRU Questionnaire (Baseline) v8_0

6

1023259 Real-World Impact of RA
[Site number] - [Participant ID]

7. In the last 6 months, have you taken any medications for your rheumatoid arthritis?			
Drug name	Average number of pills per day	Dose strength	Times per month
 ₁₅ Indomethacin (Indocid)	_____	_____ mg	_____
 ₁₆ Others	_____	_____ mg	_____
Others			
 ₁₇ Steroids	_____	_____ mg	_____
 ₁₈ Stomach or gastric medications	_____	_____ mg	_____

1023259 Real-World Impact of RA
[Site number] - [Participant ID]

8. In the last 6 months, were you hospitalized in relation to your rheumatoid arthritis other than surgery? If yes, how many days did you stay at the hospital for your rheumatoid arthritis?		
 No hospitalization in the last 6 months		
Most recent hospitalization Admission date:  / /  (DD/MM/YYYY)	 ₁ Intensive care unit (ICU)  ₂ General ward  ₃ Both  ₄ Other: _____	 Total days in hospital
Next hospitalization Admission date:  / /  (DD/MM/YYYY)	 ₁ Intensive care unit (ICU)  ₂ General ward  ₃ Both  ₄ Other: _____	 Total days in hospital
Next hospitalization Admission date:  / /  (DD/MM/YYYY)	 ₁ Intensive care unit (ICU)  ₂ General ward  ₃ Both  ₄ Other: _____	 Total days in hospital

1023259 Real-World Impact of RA

Site number	-	Participant ID
-------------	---	----------------

9. Please check all the medical conditions you have been diagnosed with.

- ₀ No comorbidity
- ₁ Myocardial infarction
- ₂ Congestive heart failure
- ₃ Peripheral vascular disease
- ₄ Cerebrovascular disease
- ₅ Dementia
- ₆ Chronic pulmonary disease
- ₇ Connective tissue disease
- ₈ Ulcer disease
- ₉ Mild liver disease
- ₁₀ Diabetes
- ₁₁ Hemiplegia
- ₁₂ Moderate or severe renal disease
- ₁₃ Diabetes with end-organ damage
- ₁₄ Any tumor
- ₁₅ Leukemia
- ₁₆ Lymphoma
- ₁₇ Moderate or severe liver disease
- ₁₈ Metastatic solid tumor
- ₁₉ AIDS

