- ₈ 5,500,000 - 6,499,999 KRW
- ₉ 6,500,000 - 9,999,999 KRW
- ₁₀ 10,000,000 + KRW
- ₀ Prefer not to tell

1023259 Real-World Impact of RA

Site number	-	Participant ID
-------------	---	----------------

Thank you for completing the Healthcare Resource Utilization Questionnaire.
Please return this form to the IMS representative.

Follow-up:

1023059 Real-World Impact of RA					
Site number	Participant ID				

[figure not shown]
Healthcare Resource Utilization & Demographic Questionnaire **(Follow-up)**

Patient ID	 - 	 Site #	 Participant #	
Today's date	 /  / 	 Day	 Month	 Year

<Request on entering>

1. Please use ballpoint pen.
2. On selecting the item, please check surely in or enter into ().
3. On correcting, please cross out with a double line (=) and **initial and date**.

102329 Real-World Impact of RA
[Site number] - [Participant ID]

1. Since you last filled out this questionnaire, did you have any consultations/visits to healthcare professionals for treatment of your rheumatoid arthritis? (Check all that apply)

₀ No visit since you last filled out this questionnaire

₁ Yes → ₁ General Practitioner
(**Taiwan:** Family Medicine) _____ times

₂ Rheumatologist _____ times

₃ Gerontologist _____ times

₄ Orthopedist _____ times

₅ Internist _____ times

₆ Emergency department _____ times

₇ Traditional Medicine _____ times

₈ Physical therapist
(**Taiwan:** Rehabilitation Medicine) _____ times

₉ Other: _____ times

1023259 Real-World Impact of RA
[Site number] - [Participant ID]

2. Since you last filled out this questionnaire, when you visited the healthcare professional(s) for treatment of your rheumatoid arthritis, were there any procedures performed?

₀ No, consultation only

₁ Yes → ₁ Chest X-Ray _____ times
 ₂ Spine X-Ray _____ times
 ₃ Neck X-Ray _____ times

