 ₁ Auranofin (Ridaura, Myochrysine)	_____	_____ mg	_____
 ₂ Azathioprine (Imuran)	_____	_____ mg	_____
 ₃ Cyclosporine (Sandimmune and Neoral)	_____	_____ mg	_____
 ₄ Hydroxychloroquine (Plaquenil)	_____	_____ mg	_____
 ₅ Leflunomide (Arava)	_____	_____ mg	_____
 ₆ Methotrexate (Rheumatrex, Folex)	_____	_____ mg	_____
 ₇ Minocycline (Minocin, Dynacin and Vectrin)	_____	_____ mg	_____
 ₈ Sulfasalazine (Azulfidine)	_____	_____ mg	_____
 ₉ Others	_____	_____ mg	_____
Anti-inflammatory Drug (NSAID)			
 ₁₀ Ibuprofen (Advil, Motrin, Nuprin)	_____	_____ mg	_____
 ₁₁ Naproxen (Naprosyn, Anaprox, Aleve)	_____	_____ mg	_____
 ₁₂ Celecoxib (Celebrex)	_____	_____ mg	_____
 ₁₃ Aspirin (ASA)	_____	_____ mg	_____
 ₁₄ Diclofenac (Voltaren)	_____	_____ mg	_____

1023259 HCRU Questionnaire (Follow-up) v8_0

6

1023259 Real-World Impact of RA
[REDACTED]
Site number - Participant ID

6. Since you last filled out this questionnaire, have you taken any medications for your rheumatoid arthritis?			
Drug name	Average number of pills per day	Dose strength	Times per month
 ₁₅ Indomethacin (Indocid)	_____	_____ mg	_____
 ₁₆ Others	_____	_____ mg	_____
Others			
 ₁₇ Steroids	_____	_____ mg	_____
 ₁₈ Stomach or gastric medications	_____	_____ mg	_____

1023259 Real-World Impact of RA

Site number	-	Participant ID
-------------	---	----------------

7. Since you last filled out this questionnaire, when you were hospitalized in relation to your rheumatoid arthritis, how many days did you stay at the hospital for your rheumatoid arthritis		
 No hospitalization since you last filled out this questionnaire		
Most recent hospitalization Admission date:   /   /   (DD/MM/YYYY)	 1 Intensive care unit (ICU)  2 General ward  3 Both  4 Other: _____	 Total days in hospital

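### Baseline healthcare resource use is a listed secondary variable, but the SAP tabulates only use after initiation; the baseline patient form also asks about 6 months where the protocol text says 3

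*Protocol*

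**What the plan says.** **Collection and status.** The schedule of events (Protocol 9.1.1) has the HCRU questionnaire at baseline, Week 12, Week 24 and early termination. Protocol 4.0 and 9.3 list HCRU at baseline, 12 and 24 weeks among the secondary variables. Protocol 7.0 and SAP 1.1 close with an aim to assess the effect of adalimumab on HCRU among other outcomes, and step 3 in the Protocol 4.0 abstract speaks of economic changes.

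**Analysis.** Protocol 9.7.6 and SAP 2.3 treat HCRU as exploratory and descriptive. SAP 3.5 summarises it over the 6 months after initiation. SAP 5.5 and the table list in SAP 6 give it one table, Table 9, which is titled as post-index. The baseline measures in SAP 5.2 are demographics, insurance, DAS28 and comorbidities.

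**Recall.** Protocol 9.2.4.7 states: "The HCRU questionnaire will collect data on the healthcare resources consumed in the prior 3 months, as recall beyond 3 months may be problematic". The baseline form in Appendix J asks "In the last 6 months, were there any consultations/visits to healthcare professionals for treatment of your rheumatoid arthritis" and "In the last 6 months, when you visited the healthcare professional(s) for treatment of your rheumatoid arthritis, were there any procedures performed". The follow-up form asks "Since you last filled out this questionnaire, did you have any consultations/visits to healthcare professionals for treatment of your rheumatoid arthritis".

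**Hospital stays.** The baseline item reads "In the last 6 months, were you hospitalized in relation to your rheumatoid arthritis other than surgery". The follow-up item reads "Since you last filled out this questionnaire, when you were hospitalized in relation to your rheumatoid arthritis, how many days did you stay" and has no exclusion for surgery.

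**Clinician source.** Under Protocol 9.2.4.6 physicians also "complete a clinical CRF in paper form based on the patient's medical records at baseline, 12 weeks, and 24 weeks". That form covers RA medications and surgeries at baseline and follow-up; for example, baseline item 7 reads "Please check all the prior medications this patient has received for her/his Rheumatoid Arthritis in the last 6 months".

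**The concern.** The study has no control group, so the period before initiation is its only internal comparator for resource use. The protocol goes to the trouble of collecting it and even excludes patients who may not report prior use accurately (Protocol 9.2.2). A table of post-initiation use alone shows neither an effect nor a change, although the background sections of both documents use that language and give reimbursement evidence as the purpose.

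The recall conflict matters for whichever baseline figures are reported. The protocol gives its own reason for stopping at 3 months, and its form goes past that limit. The two hospitalisation items would also count different things if placed side by side.

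**Working it through.** No design figure is at issue, so there is no stated number to reproduce. The check sets the texts side by side and compares window lengths.

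**1. Reporting trail**
- Protocol 4.0 and 9.3: secondary variable at three times.
- Protocol 9.7.6 and SAP 2.3: exploratory, number and percentage, no period stated. Neither excludes baseline.
- SAP 3.5, 5.5 and 6: after initiation only, with Weeks 12 and 24 pooled.
- SAP 5.2: no HCRU among the listed baseline measures.

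The restriction therefore comes from SAP 3.5, 5.5 and 6, and it conflicts with the protocol's variable list.

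**2. Recall windows** (1 month = 365.25/12 = 30.44 days)
- Protocol text: 3 × 30.44 = 91.3 days.
- Baseline patient form: 6 × 30.44 = 182.6 days, twice the stated limit.
- Follow-up forms: 84 days each nominally. With the ±7-day windows, the first covers 77 to 91 days and the second 161 − 91 = 70 to 175 − 77 = 98 days.
- If the Week 12 form is missed, which Protocol 12.6 allows, the Week 24 form reaches back 161 to 175 days. The pooled total does not change, but recall is again beyond 3 months.

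**3. Would a before-after table be distorted by window length?** Assume a constant true rate and full follow-up.
- Pooled follow-up against baseline: 1 − 168/182.6 = 8.0% fewer raw events. For a Week 24 form on day 161 it is 1 − 161/182.6 = 11.8%, and on day 175 it is 1 − 175/182.6 = 4.2%.
- One 12-week form against baseline: 1 − 84/182.6 = 54.0% fewer. Separate Week 12 and Week 24 columns therefore need rates.
- SAP Table 9 mainly reports patients with at least one event. With Poisson events, the percentage is 1 − exp(−rate × months). The rates below are assumptions:

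| Events per month | 182.6 days | 168 days |
|---|---|---|
| 0.02 | 11.3% | 10.5% |
| 0.1 | 45.1% | 42.4% |
| 0.25 | 77.7% | 74.8% |
| 1 | 99.8% | 99.6% |

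Across days 161 to 175 and these rates the gap is 0.1 to 4.6 percentage points. The pooled windows are close enough for a description.

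**4. Which items rest on recall?** Surgeries and RA medications are also on the records-based clinician form (Appendix C). Consultations, procedures and non-surgical stays rest on the patient form alone.

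**5. Eligibility work-up.** Protocol 9.2.1 (items 9 and 10) and 9.2.4.5 rely on a chest X-ray and ECG within 90 days, a laboratory profile and TB screening. Baseline percentages for chest X-ray and ECG can therefore approach 100% by design. The procedure items carry neither date nor reason, so work-up can be separated only by type of test.

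**The case against.** The formal objectives (Protocol 8.0, SAP 2) name HAQ DI, WPAI, EQ-5D and SF-36, not HCRU. A post-initiation summary satisfies SAP 2.3 as worded. A before-after contrast would carry recall that the protocol itself calls problematic, pre-treatment work-up and selection on active disease (DAS28 above 3.2), so declining it in an exploratory table is defensible. The percentages in the working describe a contrast that the SAP does not make.

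Most of this stands, and it limits the point. It does not remove the conflict between the protocol's variable list and the SAP's tables, or the conflict between the recall text and the form.

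Four stronger readings are tempting, and the documents do not support them:
- **The baseline data are discarded.** The table shells are a separate file that was not supplied, and SAP 5.1 allows tables to be modified. All that can be said is that the SAP text and table titles do not list baseline HCRU.
- **A formal objective goes unanswered.** The effect wording is in the background sections and the wording on change is in an abstract step; neither is in the formal objectives.
- **The planned HCRU results are biased by a known amount.** The 8% applies only if raw counts are set side by side. The documents give no size for recall loss and no exit times for early leavers, so any percentage for these would illustrate an assumption.
- **The clinician form breaks the recall rule too.** It is completed from medical records, so its 6-month window does not depend on patient recall.

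**Conclusion.** The point holds in limited form. As the SAP text stands, a protocol-listed secondary variable is not reported at baseline, and post-initiation use has no comparator in a single-arm study. The 3-month statement and the 6-month baseline form contradict each other, and the two hospitalisation items differ in scope. HCRU is also secondary in Protocol 4.0 and 9.3 but exploratory in Protocol 9.7.6 and SAP 2.3.

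The primary HAQ DI analysis is untouched, and importance is low to moderate. The conclusion rests on the SAP text and table titles, without the shells. The 8% figure assumes a constant rate and complete follow-up.

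**What to change.** 1. Add a baseline column to SAP Table 9, with number and percentage per category. Show Week 12 and Week 24 separately, as the protocol lists them, or state that they are pooled.
2. For count items, also give events per patient-month of each patient's actual window.
3. Take surgeries and RA medications from the clinician CRF at both times. At baseline use the 6-month medication list (item 7), not the current list (item 11).
4. Compare only non-surgical stays, using CRF surgery dates to identify surgical ones. SAP 3.5.5 sets a missing day to 15, so leave stays that depend on an imputed day unclassified, or test them in a sensitivity check.
5. Show chest X-ray, ECG, laboratory and TB tests separately, by item type.
6. Label the result an uncontrolled before-after description, limited by 6-month recall, pre-treatment work-up and selection on active disease.
7. Reconcile Protocol 9.2.4.7 with Appendix J, state the recall period used, and settle whether HCRU is secondary or exploratory.

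If the baseline column is not wanted, amend the variable lists in Protocol 4.0 and 9.3, abstract step 3, Protocol 7.0 and SAP 1.1 so that they describe post-initiation use only. Item 7 is still needed.

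Cost: SAP wording and modest extra programming on data already planned for collection, with no form change. Recall error in the patient-only baseline items remains, and rates do not remove it. Narrowing the wording is cheaper but gives up the only internal comparator.

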9.2.5 Adverse Events

Adverse events, whether in response to a query, observed by site personnel, or reported spontaneously by the subject will be recorded. Adverse events definition and serious adverse event categories are described in detail in Section 11.0.

9.2.6 Removal of Subjects from Therapy or Assessment

1. Discontinuation of Individual Subjects

A subject may withdraw from the study at any time. The Investigator may discontinue any subject's participation for any reason, including an adverse event, safety concerns or failure to comply with the protocol.

Subjects will be withdrawn from the study immediately if any one of the following occurs:

- Clinically significant abnormal laboratory result(s) or adverse event(s), as determined by the Investigator in consultation with the AbbVie Medical Monitor.
- The Investigator believes it is in the best interest of the subject.
- The subject requests withdrawal from the study.
- Inclusion and exclusion criteria violation was noted after the subject started study drug, when continuation of the study drug would place the subject at risk as determined by the AbbVie Medical Monitor (see *Section 5.2* and *Section 7.0*).
- Introduction of prohibited medications or dosages when continuation of adalimumab would place the subject at risk as determined by the AbbVie Medical Monitor.
- Subject is non-compliant with TB prophylaxis.
- The subject becomes pregnant during the study period.
- Subject has dysplasia of the gastrointestinal tract or a malignancy, except for localized non-melanoma skin cancer. Discontinuation for carcinoma in-situ of the cervix is at the discretion of the Investigator.
- Subject is diagnosed with lupus-like syndrome, multiple sclerosis or demyelinating disease.
- Subject is significantly non-compliant with clinical follow-up which would put the subject at risk for continued participation in the trial, as determined by the Investigator, in consultation with the AbbVie Medical Monitor.

The subject will be treated in accordance with the Investigator's best clinical judgment. If the subject prematurely dropped out from the study, the pre-defined Terminal Visit data should be collected within 2 weeks of the last dose of adalimumab, and preferably prior to the initiation of another therapy. However, these data collection should not interfere with the initiation of any new treatments or therapeutic modalities that the Investigator feels are necessary to treat the subject's condition. A final data of a subject will be recorded

approximately 70 days after the Week 24 dosing or the last dose of adalimumab to determine the status of any ongoing AEs/SAEs or the occurrence of any new AEs/SAEs. The information will be recorded on the appropriate in eCRF page.

For subjects that are considered lost to follow-up, reasonable attempts must be made to obtain information on the final status of the subject. At a minimum, two phone calls must be made and one certified letter must be sent.

9.3 **Variables**

Variables (as observed):

Primary Variable

- Change in HAQ DI score at week 24 from baseline

Secondary Variable

- Change in other PROs (SF-36 domain scales, EQ-5D Index, Work Productivity and Activity Impairment Questionnaire [WPAI]) from baseline to weeks 12 and 24
- Change in HAQ DI score at week 12 from baseline
- Number and percent of patients achieving a clinically meaningful improvement on the HAQ DI, from baseline to weeks 12 and 24
- Healthcare Resource Utilization (HCRU) at baseline, 12 and 24 weeks

Exploratory Variable

- Difference of the change in HAQ DI score from baseline to 24 weeks between as observed population and withdrawal population
- Change in patient satisfaction questions from baseline to weeks 12 and 24
- Patient's impression of change at weeks 12 and 24 from baseline
- Association between disease severity and PROs
- Association between change in disease severity and change in PROs

9.4 **Data Sources**

Case Report Forms (CRFs) and patient questionnaires.

Collection of data includes but not limited to subject demographics, clinical history, comorbidities, spontaneous adverse events, and concomitant medications. The following questionnaires will be utilized to collect data directly from participating subjects:

- EQ-5D
- SF-36
- HAQ DI
- WPAI

- HCRU
- Patient Global Impression of Change (PGIC)
- Patient Treatment Satisfaction Questions

9.5 **Study Size**

Approximately 100 patients diagnosed with RA will be recruited. The planned sample size provides at least 95% power for detecting a statistically significant improvement in HAQ-DI (Δ HAQ-DI < 0) assuming a mean Δ HAQ-DI of -0.21 and a standard deviation of 0.5 (reference 11), at two-sided significance level of 0.05 and accounting for a 10% dropout rate. The sample size also provides at least 95% power for detecting a statistically significant clinically meaningful improvement in HAQ-DI (Δ HAQ-DI < -0.22) assuming a mean Δ HAQ-DI of -0.5 and a standard deviation of 0.7, at two-sided significance level of 0.05 and accounting for a 10% dropout rate. For the secondary endpoint WPAI, the sample size provides 63% power for detecting a statistically significant improvement in “hours of work lost” at two-sided significance level of 0.05 and accounting for a 10% dropout rate, assuming a mean change in “hours of work lost” of 10 and standard deviation of 30 and assuming a 55% employment rate in the study population.

9.6 **Data Management and Storage Process**

9.6.1 **Data Management**

Data management and data quality check will be performed to remove errors and inconsistencies in order to assure the appropriateness of the study data set to assess the study objectives. Data entry screens will be developed and tested prior to initiating data collection to reduce data entry errors. If required, IMS will provide AbbVie with data for analysis.

Each site coordinator will be instructed to answer patients’ queries which may arise in relation to the questionnaires and check the patients’ input to make sure all questions are answered.

9.6.2 **Storage Process**

Following data quality checks, each dataset will be converted to SAS and merged for analysis. All information included in the CRF and the patients’ questionnaires will be checked in order to detect possible queries to solve and will be extracted to a specifically designed database, where it will be validated by IMS personnel to ensure its quality. Finally, data analysis will be conducted and final results reported.

The databases will be stored in IMS data servers. Data servers are submitted to daily backups in order to increase the security on all data managed in the collection process.

All paper based questionnaires will be stored in a secured, locked area for a period of seven (7) years, after which all data will be shred using an agency specialized in disposal of confidential documents.

